5.2 Exclusion Criteria

Participants are excluded from the study if any of the following criteria apply:

Medical Conditions

1. Symptomatic local-regional disease that requires medical intervention including moderate/severe urinary obstruction or hydronephrosis with abnormal renal function due to prostate cancer. Participants with visceral metastasis will be excluded.
2. Severe or uncontrolled concurrent disease, infection, or comorbidity
3. Past (within 6 months before the start of study intervention) or concurrent stroke, myocardial infarction, severe/unstable angina pectoris, coronary/peripheral artery bypass graft, and/or congestive heart failure (New York Heart Association Class III or IV)
4. Uncontrolled clinically significant hypertension
5. Prior malignancy. Adequately treated basal cell or squamous cell carcinoma of the skin or superficial bladder cancer that has not spread behind the connective tissue layer (i.e. pTis, pTa, and pT1) is allowed, as well as any other cancer for which treatment has been completed 3 years before the start of study intervention and from which the participant has been disease free
6. Known metastatic brain or meningeal tumors
7. Prior or concurrent central nervous system disease, such as epilepsy, Parkinson's disease, Alzheimer's disease, dementia, or multiple sclerosis
8. Active viral hepatitis, active human immunodeficiency virus (HIV), or chronic liver disease
9. Gastrointestinal disorder or procedure that is expected to interfere significantly with absorption of study treatment
10. Major surgical procedure or significant traumatic injury within 28 days before the start of study intervention

11. Seizure disorder requiring medication
12. Non-healing wound, ulcer, or bone fracture
13. Substance abuse, medical, psychological, or social conditions that may interfere with the participant's participation in the study or evaluation of the study results
14. Non-ambulatory participants who need a wheelchair. Other assistive devices (e.g., cane or walker) are permitted.
15. Any illness or medical condition that is unstable or could jeopardize the safety of the participant and his compliance in the study
16. Clinically significant limitations in cognitive function and/or physical function, such as >20 seconds in the TUG assessment

Prior/Concomitant Therapy

17. Prior treatment with any of the following:
 - Second-generation AR inhibitors, such as enzalutamide, apalutamide, or darolutamide

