Trail Making Test (TMT) Part A (TMTA) Part B (TMTB)	The TMT Part A (TMTA) assesses visual scanning and motor tracking requiring focused attention. Participants are required to sequentially connect numbered dots in ascending order that are randomly scattered across the test page. Part B (TMTB) includes a divided attention component requiring mental flexibility (i.e., executive function). On this subtest, dots with numbers and	1–2750 seconds 1–3750 seconds	±12 seconds ±26 seconds (Wefel et al. 2011)

Test	Description	Possible range of score	MCID / RCI from baseline
	
letters are randomly scattered on the test page. Participants are required to alternate between connecting numbers and letters in an ascending sequential order.
 
Both tests require the participants to complete the sequence as fast as possible. TMTA is discontinued after 3 minutes and TMTB is discontinued after 5 minutes for participants who have difficulty in order to reduce participant burden.
		
Controlled Oral Word Association (COWA)	The COWA test assesses lexical fluency. Given a specific letter of the alphabet, participants are required to produce as many words as possible that begin with that letter. There are two alternate forms of the COWA, each with three unique letter exemplars.	0 – unlimited words	±12 words (Wefel et al. 2011)
Cognitive tests – Patient-reported outcomes			
Functional Assessment of Cancer Therapy-Cognitive (FACT-Cog)	The FACT-Cog questionnaire was developed to assess perceived cognitive function and impact on quality of life (QOL) in cancer patients. It is a patient-reported outcome measure used to assess cognitive function in patients undergoing cancer therapy.	0–28 points	6.9-10.6 points (Cheung et al. 2014, Costa et al. 2018)

COWA = Controlled Oral Word Association; FACT-Cog = Functional Assessment of Cancer Therapy-Cognitive; HVLTR DR = Hopkins Verbal Learning Test-Revised Delayed Recall; HVLTR RECOG = Hopkins Verbal Learning Test-Revised Delayed Recognition; HVLTR TR = Hopkins Verbal Learning Test-Revised Total Recall; MCID = minimal clinically important difference; QOL = quality of life; RCI = reliable change index; SPPB = Short Physical Performance Battery; TMTA/TMTB = Trail Making Test Part A/B; TUG = Timed up & Go

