### Cognitive function

- The proportion of participants with a decline in cognitive function at 24 and within 52 weeks as assessed by HVLTR, TMT, and COWA, will be summarized. At each assessment, the change in score from baseline will be calculated and the status of cognitive function will be categorized as improved, stable, or declined using the Reliable Change Index (RCI) as shown below. Each test will be assessed individually. The proportion of participants with a decline and exact 95% CIs will be summarized. For the randomization phase, the proportion of subjects with a decline will be summarized separately by treatment arm, and a comparison between arms at week 24 and week 52 will be made using CMH test adjusting for Age (<75, ≥75).

Test	Reliable Change Index threshold (from baseline)
Hopkins Verbal Learning Test - Revised Total Recall (HVLTR TR)	±5 words HVLTR TR has a range of 0-36, recalling a list of 12 words over 3 trials.
Hopkins Verbal Learning Test - Revised Delayed Recall (HVLTR DR)	±3 words HVLTR DR has a range of 0-12.
Hopkins Verbal Learning Test - Revised Delayed Recognition (HVLTR RECOG)	±2 words HVLTR RECOG has a range of -12 to 12 words. It is equal to true positives (subject says 'yes' to 12 original words on list) minus false positives (subjects says 'yes' to distractors [12 words not on original list]).
Trail Making Test: Part A (TMTA)	±12 seconds TMT Part A is timed up to a maximum of 3 minutes. If not completed in the given amount of time, the subject is assigned a time equal to the maximum time.
Trail Making Test: Part B (TMTB)	±26 seconds

	TMT Part B is timed up to a maximum of 5 minutes. If not completed in the given amount of time, the subject is assigned a time equal to the maximum time.
Controlled Oral Word Association (COWA)	±12 words Subjects are asked to name as many words as possible all beginning with a specified letter. A total of three trials are administered, and the score on the COWA is the total number of words named across the three trials.

- The proportion of participants with a decline of >10 points from baseline in the FACT-Cog domain at 24 and within 52 weeks will be summarized in a similar fashion.

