**Table 4 Study Assessments for Physical Ability and Cognitive Function**

Test	Description	Possible Range of score	MCID/RCI from Baseline
Physical ability tests			
Timed Up and Go (TUG)	The TUG test is used to assess a person's mobility and requires both static and dynamic balance. It uses the time that a person takes to rise from a chair, walk three meters, turn around, walk back to the chair, and sit down.  Where possible, TUG time is to be measured by independent blinded assessors.	>1 second	1 second (Davies et al. 2016) [1]
Short Physical Performance Battery (SPPB)	The SPPB is a group of measures that combines the results of the gait speed, chair stand and balance tests.	0–12 points	0.5 points (Davies et al. 2016) [1]
Cognitive Tests			

Test	Description	Possible Range of score	MCID/RCI from Baseline
Hopkins Verbal Learning Test-Revised Total Recall (HVLTR TR)	The HVLTR is a learning and memory test, in which the participant is asked to learn and recall a list of 12 words over 3 trials.	0–36 words	±5 words (Wefel et al. 2011) [4]
Hopkins Verbal Learning Test-Revised Delayed Recall (HVLTR DR)	Spontaneous recall is assessed before and after a delay.	0–12 words	±3 words (Wefel et al. 2011) [4]
Hopkins Verbal Learning Test-Revised Delayed Recognition (HVLTR RECOG)	Recognition discriminability is also assessed after a delay. Four alternate versions of the test are used to minimize practice effects over time.	-12–+12 words	±2 words (Wefel et al. 2011) [4]
Trail Making Test (TMT) Part A (TMTA) Part B (TMTB)	
The TMTA assesses visual scanning and motor tracking requiring focused attention. Participants are required to sequentially connect numbered dots in ascending order that are randomly scattered across the test page.
 
TMTB includes a divided attention component requiring mental flexibility (i.e., executive function). On this subtest, dots with numbers and letters are randomly scattered on the test page. Participants are required to alternate between connecting numbers and letters in an ascending sequential order.
 
Both tests require the participants to complete the sequence as fast as possible. TMTA is discontinued after 3 minutes and TMTB is discontinued after 5 minutes for participants who have difficulty in order to reduce participant burden.
	1–2750 seconds 1–3750 seconds	±12 seconds ±26 seconds (Wefel et al. 2011) [4]

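### Capped Trail Making times leave a band of slow baselines (above 168 s on Part A, above 274 s on Part B) in which losing the ability to finish is scored as stable

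*SAP*

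**What the plan says.** The scoring table under Cognitive function in SAP 5.5.2 sets the two limits: "TMT Part A is timed up to a maximum of 3 minutes" and "TMT Part B is timed up to a maximum of 5 minutes". For each part it adds the same rule for a man who does not get through: "If not completed in the given amount of time, the subject is assigned a time equal to the maximum time". The reliable-change thresholds in that table are ±12 seconds for Part A and ±26 seconds for Part B.

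Status follows from the change alone: "the change in score from baseline will be calculated and the status of cognitive function will be categorized as improved, stable, or declined". There is no separate category for non-completion. In the randomized phase the decline proportions are compared between arms with a CMH test adjusted for age.

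The protocol stops the tests at the same times (Table 8–1 in section 8.2): "TMTA is discontinued after 3 minutes and TMTB is discontinued after 5 minutes for participants who have difficulty in order to reduce participant burden". Yet Protocol Table 8–1 and SAP Table 4 both print the possible score ranges as "1–2750 seconds 1–3750 seconds".

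The only endpoint-specific missing-data rule, in SAP 4.2, concerns TUG. SAP Table 3 keeps every treated man with a baseline and at least one post-baseline assessment in the analysis of each instrument.

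**The concern.** A longer time is a worse result, so decline means a rise of about 12 s or 26 s. The cap limits how far a time can rise. For a man already close to it, the remaining room is smaller than the threshold, and the clearest sign of worsening that the test can give (he could finish before and now cannot) is recorded as no change. He stays in the denominator, so the decline rate can only be pushed down.

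Two of the six cognitive measures in SAP 5.5.2 are affected. Protocol 4.1 also names decline on HVLT-R and TMT among the endpoints evaluated at the end of the lead-in, before the randomized-phase endpoint and sample size are settled. With about 30 men in that phase, each man classed differently moves a rate by 1/30 = 3.3 percentage points.

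**Working it through.** The plan states no sample size, power or expected rate for Trail Making, so there is no figure of its own to reproduce. The check applies its scoring rules.

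**Inputs from SAP 5.5.2.** Cap: 3 min = 180 s (A), 5 min = 300 s (B). Threshold: 12 s (A), 26 s (B). The direction, with a rise counting as worse, is inferred from the ± sign and the nature of the test.

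**Step 1. Highest baseline at which decline can be scored.** The largest recordable change is cap − baseline, so decline needs baseline ≤ cap − threshold.
- Part A: 180 − 12 = 168 s.
- Part B: 300 − 26 = 274 s.

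**Step 2. Men who cannot finish at follow-up.**

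| Part | Baseline (s) | Assigned at follow-up (s) | Change (s) | Status as written |
|---|---|---|---|---|
| A | 160 | 180 | +20 | declined |
| A | 170 | 180 | +10 | stable |
| A | 180 (at cap) | 180 | 0 | stable |
| B | 266 | 300 | +34 | declined |
| B | 280 | 300 | +20 | stable |
| B | 300 (at cap) | 300 | 0 | stable |

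At exactly 168 s or 274 s the result depends on whether the threshold is inclusive, which the SAP does not say. A man at the cap at baseline can still improve: 300 s and then 250 s is −50 s. He can never be scored as declined.

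**Step 3. How many men could be in the Part B band.** The documents give no baseline times. As an assumption, take log-normal times with log-SD 0.45 and a range of medians. The share above t is 1 − Φ(ln(t/median)/0.45).

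| Assumed median (s) | Above 274 s | Above 300 s | 274 to 300 s |
|---|---|---|---|
| 110 | 2.1% | 1.3% | 0.8% |
| 130 | 4.9% | 3.2% | 1.7% |
| 150 | 9.0% | 6.2% | 2.9% |
| 180 | 17.5% | 12.8% | 4.7% |

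The last column is the group that finishes at baseline and could later fail without being counted. The model ignores the exclusion criteria. Part A was not modelled.

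**Step 4. Outer bound on dilution.** Suppose a true difference of 10% versus 25% (an assumption) and suppose every decline above 274 s is missed, including among men already at the cap. The difference then reads (1 − share above 274 s) × 15 = 14.7, 14.3, 13.6 or 12.4 points, a loss of 0.3 to 2.6 points. With 120 × 0.9 / 2 = 54 men per arm, the standard error is √(0.10 × 0.90/54 + 0.25 × 0.75/54) = 0.072, or 7.2 points.

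**The case against.** **Status is censored, not shown to be wrong.** For the man at 280 s who then fails, the true change is known only to exceed 20 s. It could be 22 s, which is stable under the SAP's own threshold. This stands. A reader might infer that the rule demonstrably misclassifies these men, and the documents do not support that. What they show is that an unknown status is always resolved as stable.

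**Eligibility thins the band.** Protocol 5.2 excludes dementia and other central nervous system disease (criterion 7), "Clinically significant limitations in cognitive function and/or physical function, such as >20 seconds in the TUG assessment" (criterion 16), and men whom the investigator judges unable to do the tests (criterion 26). This largely stands and argues for a small number. It does not empty the band: no Trail Making cut-off is set, and cognitive testing is first scheduled at Week 1 Day 1, not at screening.

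**Most of the model's upper tail is not the case at issue.** Between 61 and 73% of the men it places above 274 s are above 300 s, so they already fail at baseline, the group that criterion 26 addresses. This stands, and it is why the 2.1 to 17.5% column should not be read as the share affected by newly lost completion.

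**Every bounded scale has a floor.** A man recalling fewer than 3 words on HVLT-R delayed recall cannot lose 3 either. That is true, but there the recorded score is his actual score. Here an observed failure is replaced by a number and then called stable.

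**The band is fixed before treatment.** Randomization balances it in expectation, so it creates no false difference between arms. This stands. The effect is under-counting and some dilution.

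**Conclusion.** The point holds for a defined group. As written, a man with a baseline above 168 s (Part A) or 274 s (Part B) cannot be scored as declined, even if he goes from finishing to not finishing, and no other rule in either document catches him.

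Two broader readings are tempting and do not hold. One is that non-completers in general are called stable; below those baselines they are scored as declined. The other is that a man at the cap at baseline is stable whatever happens; he can be scored as improved.

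The size is probably small: about 0.8 to 4.7% of men in the 274 to 300 s band, on assumed log-normal times that the documents neither support nor contradict and before any effect of the exclusions. Even the outer bound on dilution is well below one standard error of the arm difference. The direction is toward under-counting decline on a secondary endpoint. This is a low-priority correction, worth making because it is cheap and because Trail Making decline is reviewed at the end of the lead-in.

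**What to change.** In SAP 5.5.2, after the Trail Making rows, add: a participant who finished a part within the limit at baseline but not at a follow-up visit is classed as declined on that part at that visit; a sensitivity analysis uses the assigned maximum time and the change threshold alone.

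State in the same place whether the ±12 s and ±26 s thresholds are inclusive. Keep men at the cap at baseline in the analysis set defined in SAP Table 3 and report their number by arm. Dropping them would depart from that set and would also lose men who can validly improve.

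As a tidy-up, reconcile the printed ranges in SAP Table 4 and Protocol Table 8–1 with the 180 s and 300 s limits.

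**Cost.** A few lines in the SAP and one extra summary. A man just under the cap at baseline, say 295 s, may be counted as declined on a true slowing of little more than 5 s; the sensitivity analysis shows how much this matters. The rule also needs completion status to be identifiable in the data, so that a finish at exactly 300 s can be told from an assigned 300 s. The documents do not show whether the CRF records this, and it should be checked first.

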### Fatigue

- The proportion of participants with an increase of at least 1 point in worst level of fatigue from baseline during the past 24 hours (item 3 of BFI) within the first 24 weeks, and during the entire 52 week period will be summarized. Exact 95% CI will also be presented, and a comparison between arms will be made using CMH test adjusting for Age (<75, ≥75) for the randomization phase.
- Similarly, the proportion of participants with an increase of at least 1 point in fatigue interference from baseline during the past 24 hours (items 4A through F of BFI) by 24 and 52 weeks will be summarized. The proportion of participants with a decline and the 95% CIs will be summarized, and for the randomization phase proportions will be reported by treatment arm. A comparison between arms will be made using a CMH test adjusting for Age (<75, ≥75).

### Depression

The proportion of participants with a worsening of scores by PHQ-9 within the first 24 weeks and during the entire 52 week period from baseline will be summarized. Worsening is defined as an increase of at least 1 point in worst level of depression from baseline by 24 weeks and 52 weeks.

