In addition, fatigue will be assessed using BFI. BFI is a validated tool and consists of three questions assessing the severity of fatigue and six questions assessing the impact of fatigue on the participant's mood, social functioning and physical functioning. The BFI is a 9-item scale developed to assess subjective fatigue. Each question is asked in relation to the last 24 hours and is scored on an 11-point numerical rating scale, with higher scores indicating greater fatigue and interference with functionality. The first three questions measure fatigue severity at current, usual, and worst levels from 0 to 10, with 0 indicating "no fatigue," and 10 indicating "as bad as you can imagine". The following six questions assess fatigue interference with daily activities including general activity, mood, walking ability, normal work (both inside and outside the home), relations with other people, and enjoyment of life. Response options range from 0 to 10 with 0 indicating "does not interfere" and 10 indicating "completely interferes." Higher scores on the BFI correspond to greater self-reported levels of fatigue.

Depression will be assessed using PHQ-9. It is a self-administered version of the Primary Care Evaluation of Mental Disorders (PRIME-MD) diagnostic instrument for common mental

disorders. The PHQ-9 is the depression module, which scores each of the 9 Diagnostic and Statistical Manual of Mental Disorders (DSM-IV) criteria as “0” (not at all) to “3” (nearly every day) (Kroenke et al. 2001). As a severity measure, the PHQ-9 score can range from 0 to 27, since each of the 9 items can be scored from 0 (not at all) to 3 (nearly every day). Major depression is diagnosed if 5 or more of the 9 depressive symptom criteria have been present at least “more than half the days” in the past 2 weeks, and 1 of the symptoms is depressed mood or anhedonia. Other depression is diagnosed if 2, 3, or 4 depressive symptoms have been present at least “more than half the days” in the past 2 weeks, and 1 of the symptoms is depressed mood or anhedonia. One of the 9 symptom criteria (“thoughts that you would be better off dead or of hurting yourself in some way”) counts if present at all, regardless of duration.

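### PHQ-9 worsening is defined on an ambiguous score with a 1-point cumulative threshold and no planned between-arm test; name the total score and pre-specify a baseline-adjusted comparison

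*SAP*

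**What the plan says.** SAP 5.5.2 (Depression) defines PHQ-9 worsening as "an increase of at least 1 point in worst level of depression from baseline", assessed by Week 24 and by Week 52. Protocol 9.4.2, and the endpoint tables in Protocol 1.1 and 3, use the same definition, so this is not a slip in the SAP alone. The window is cumulative: the SAP says that the proportion who worsen "within the first 24 weeks and during the entire 52 week period from baseline will be summarized".

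The only description of the instrument is in Protocol 8.2: nine items, each scored 0 to 3, so that "the PHQ-9 score can range from 0 to 27". The same section describes the BFI, and there a worst level does exist: "The first three questions measure fatigue severity at current, usual, and worst levels from 0 to 10". SAP 5.5.2 (Fatigue) ties "an increase of at least 1 point in worst level of fatigue from baseline" to item 3 of the BFI. The depression sentence has the same construction.

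The schedules of activities collect the PHQ-9 at Week 1 Day 1 and at Weeks 4, 8, 12, 24 and 52, with none at Week 38. The secondary objective (Protocol 1.1 and 3; SAP Table 1) is to compare the arms on depression. SAP 5.5.2 names a CMH test for the cognitive and fatigue endpoints but none for the PHQ-9. Under the general rules of SAP 5.1, the PHQ-9 gets descriptive change from baseline by time point, and proportions with 95% CIs.

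**The concern.** There are three separate weaknesses.

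- **The score is not identified.** A programmer could take the worst post-baseline total, the highest of the nine items, or a severity category. These give different event rates. In an open-label trial, choosing among them after data are available would be post hoc.
- **The threshold is the smallest possible step, counted cumulatively.** On the total, one step on one item at one of four visits by Week 24 (five by Week 52) is enough, with no confirmation. The documents cite no source for 1 point, whereas the TUG and cognitive thresholds carry citations. Random fluctuation alone then produces events in both arms, which shrinks any real difference.
- **The stated objective has no matching analysis.** The objective is comparative, but the depression paragraph plans only a summary.

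At stake is whether the depression objective can be read clearly in the randomized phase.

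**Working it through.** **1. The plan's own figure.** The documents give no rate, variability or power for the PHQ-9. The only stated power is for TUG: 85% for 20% vs 40%, about 120 randomized, one-sided 10%, 10% drop-out (SAP 3.4). Evaluable n per arm = 120 × 0.9 / 2 = 54.

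Power = Φ{(|p₁−p₂|√n − z√(2p̄q̄)) / √(p₁q₁+p₂q₂)} = Φ{(0.2×7.348 − 1.2816×0.648)/0.632} = Φ(1.01) = 84.4%.

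This reproduces the 85%, and 54 per arm is used below.

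**2. Ceiling for stable participants.** If true status does not change and repeat scores are exchangeable, the chance that at least one of k later scores exceeds baseline is at most k/(k+1): 4/5 = 80% by Week 24 and 5/6 = 83% by Week 52. Ties and a floor at zero lower it.

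**3. Simulated share of stable participants counted as worse.** All PHQ-9 inputs here are assumptions.

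| Model | Reading | By Week 24 | By Week 52 |
|---|---|---|---|
| Rounded score with noise; mean 1–7, within-person SD 0.5–2.5 | total, ≥1 point, any visit | 50–74% | 53–78% |
| Gamma-Poisson; mean 1–5 | total, ≥1 point, any visit | 59–70% | 64–74% |
| Nine-item; 28–86% at zero | total, ≥1 point, any visit | 14–61% | 15–65% |
| Nine-item; 28–86% at zero | highest single item, any visit | 9–40% | 10–44% |

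A rounded-score model with mean 4 and SD of change 2, 3 and 4 gives 70.5%, 73.8% and 75.3% by Week 24. In the nine-item model the total-score rate passes one half in only two of eight scenarios. In the first two models, a 1-point rise at the Week 24 visit alone occurs in 23–41%.

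**4. Dilution.** If a fraction f of participants who have not truly worsened are counted as worse in both arms, the observed rate is t + (1−t)f, and the arm difference shrinks by the factor (1−f). The TUG contrast is borrowed below purely as an illustration (54 per arm, one-sided 10%).

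| f | Observed rates | Power |
|---|---|---|
| 0 | 20% vs 40% | 84% |
| 0.2 | 36% vs 52% | 66% |
| 0.5 | 60% vs 70% | 42% |
| 0.7 | 76% vs 82% | 30% |
| 0.8 | 84% vs 88% | 25% |

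**5. Alternative analysis.** Assumptions: total-score reading, gamma-distributed true score with mean 4, rounding and a floor at zero, a constant 1.5-point arm difference at every post-baseline visit, 54 per arm, two-sided 5%. Ranges cover repeat simulations with slightly different settings.

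| SD of change | Any-visit 1-point proportion by Week 24 | Baseline-adjusted change at Week 24 |
|---|---|---|
| 2 | 83–85% | 97–99% |
| 3 | 53–55% | 79–80% |
| 4 | 33–35% | 56–61% |

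Hand check, unadjusted change: Φ{1.5/(SD√(2/54)) − 1.96} = Φ(1.94), Φ(0.64) and Φ(−0.01) = 97%, 74% and 50%. The adjusted figures should lie near or above these, and they do.

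At one-sided 10% the proportion has about 96%, 79% and 61–63%, and adjusted change about 99%, 92–93% and 78–81%. The ordering is the same.

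**The case against.** The strongest reply is that this is a wording slip on one of many secondary endpoints in a Phase 2b trial powered on TUG. The SAP paragraph begins by referring to PHQ-9 scores, and Protocol 8.2 gives one severity score. Read with a cumulative window, a worst level is most easily the highest post-baseline total, which can be programmed. That stands: the rule is ambiguous, and a reader who infers that the endpoint cannot be computed goes too far.

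A reader might also infer that most stable participants would be counted as worse. The documents give no PHQ-9 baseline level or variability, and the share falls well below half if many participants score zero or if the highest item is meant. The any-visit rule is itself an inference: the SAP writes it out for TUG and SPPB but not for the PHQ-9.

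Nor does the rule hide a real difference. It loses power, and at SD 2 it still has 83–85% at two-sided 5%. The 1.5-point effect has no source in the documents.

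Part of what is wanted is already planned, since SAP 5.1 covers descriptive change from baseline by arm. A between-arm comparison also arises only if the randomized phase goes ahead, after its endpoints and sample size have been reassessed. These points limit the consequence. They do not settle which score is meant, where the 1-point threshold comes from, or why depression alone lacks the test that fatigue and cognition have.

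**Conclusion.** The point holds as an ambiguous definition combined with an inefficient, unsourced rule and a missing comparison. The ambiguity and the missing test are textual and need no assumptions. The size does: about 14–75% of stable participants counted as worse by Week 24 on the total-score reading and 9–40% on the single-item reading, so a large share and possibly a majority. Under the assumptions in step 5, the any-visit proportion gives up roughly 12 to 28 percentage points of power against baseline-adjusted change (at the extremes, 97−85 = 12 and 61−33 = 28). The two analyses summarize different quantities, so this is an argument for adding the second, not for deleting the first.

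A reader might extend the criticism to BFI item 3. The documents do not support that: the item exists, it is correctly identified, it already has exact CIs and a CMH test, and no calculation here addresses it. The primary TUG analysis is not touched. This should be corrected, but it does not threaten the trial's main conclusion.

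**What to change.** In SAP Table 1 and 5.5.2, replace the reference to a worst level of depression with the PHQ-9 total score (0–27), and state that the 1-point proportion counts a rise at any scheduled visit in the window. Keep that proportion, with its 95% CI, as descriptive.

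For the randomized phase, pre-specify a between-arm comparison of change in PHQ-9 total at Weeks 24 and 52, adjusted for baseline score and age stratum (<75, ≥75), reporting the adjusted difference with its 95% CI. Make the same wording correction in Protocol 1.1, 3 and 9.4.2 at the next amendment, or record the change in SAP 6.0, which now lists none.

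The cost is a text edit and one model on data already collected: no new visits, instruments or participants. It adds one more secondary comparison at two time points, which should be reported as supportive. It should be settled before any randomized-phase PHQ-9 data are examined.
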